#### **2.4.7.1.2 Treatment-emergent adverse events**

An overview of TEAEs will be provided to include (potentially related is defined as either “related” or “possibly related” as assessed by the investigator):

- TEAEs
- TEAEs excluding original study
- TEAEs potentially related to study treatment

- TEAEs by the worst severity
- TEAEs leading to treatment discontinuation
- TEAEs leading to study withdrawal
- TEAEs leading to dose reduction
- TEAEs leading to study treatment interruption
- Protocol-defined IARs
- Algorithm-defined IARs
- Treatment-emergent serious adverse events
- Treatment-emergent serious adverse events potentially related to study treatment
- TEAEs with fatal outcome (Deaths)
- Treatment-emergent pregnancies
- TEAEs which are considered symptomatic overdose
- Dose-limiting toxicities (collected in the adverse event log page in e-CRF, see protocol Section 8.1.6 for details)

The following summaries will be produced by primary SOC and PT:

- TEAEs
- TEAEs by the worst severity (ie, mild, moderate, or severe)
- TEAEs potentially related to study treatment
- TEAEs potentially related to study treatment, by the worst severity (ie, mild, moderate, or severe)

The most common TEAEs will be summarized by SOC and PT for patients from pediatric study DFI13803 and for patients from adult study DFI13412 in separate tables. The criteria of most common TEAEs are the following, which will be applied to the two populations separately:

- the number of events of a preferred term is more than or equal to 2% of the number of all TEAEs in the population, AND
- the number of patients who had this event is more than or equal to 2.

For the above summary for patients from pediatric study, it will be summarized by age cohort and overall.

TEAEs by the latest infusion dose immediately preceding the start of AE will be provided by SOC and PT.

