### **1.2 OBJECTIVES**

#### **1.2.1 Primary objectives**

The primary objective of this study is to obtain data regarding the safety of olipudase alfa in patients with ASMD who are exposed to long-term treatment with olipudase alfa.

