## 1.5 MODIFICATIONS TO THE STATISTICAL SECTION OF THE PROTOCOL

In the section of statistical consideration of the Amended Clinical Trial Protocol 4 Section 11.6.3, treatment period is defined as time from first dose to the last dose of IMP +14 days. In this SAP, in order to incorporate the data from original study (ie, adult study DFI13412 or pediatric study DFI13803), the treatment period definition is changed to “the time from the first infusion of IMP (included) from original study to the end of the current study”.

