#### **2.4.7 Analyses of safety data**

The safety results will be presented using the safety population. Unless specified otherwise, the displays will include the original study data along with data collected in this study. Patients will be summarized and displayed by original study identifier, age cohort and overall. Safety data will be reported up to and including the time of treatment withdrawal, and follow-up for AEs, where applicable. The baseline value is the last available value before the first infusion of olipudase alfa in the original study, except for hematology parameters and possibly ECG parameters. For complete definition of baseline, refer to [Section 2.6.1](#).

For all safety data, the observation period in this study is the **on-treatment period**, which is defined as the time from the first infusion of IMP (included) from original study to the end of the current study

The following definitions regarding potentially clinically significant abnormality (PCSA) will be applied to laboratory parameters, vital signs and ECG:

- The PCSA values are defined as abnormal values considered medically important by the sponsor according to predefined criteria/thresholds based on literature review and defined by the sponsor for clinical laboratory tests, vital signs, and ECG. These values are provided in [Appendix A](#).
- PCSA criteria will determine which patients had at least 1 PCSA taking into account all evaluations performed, including unscheduled or repeated evaluations.
- Before determining a value as PCSA, the value will be rounded to the precision that the PCSA criterion is defined.

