##### **2.4.7.1 Analyses of adverse events**

###### **2.4.7.1.1 Definitions**

Adverse events continuing from the original study into the entry into this extension study will be identified, and will be reported as one AE avoiding duplication of the same AE in two database. Adverse event summaries will include the number of events (N), number (n) and percentage (%) of patients experiencing an adverse event. The denominator for computation of percentages is the safety population. Sorting order will follow the internationally agreed MedDRA system organ

class (SOC) order, and further by decreasing number of events overall in preferred terms (PTs) within SOCs. When more than one PT has same number of events within the same SOC, the order of presentation will be alphabetical in PTs.

Treatment-emergent adverse events (TEAEs) will be defined as AEs that started during the on-treatment period – either in this study or in the original study.

If an AE date/time of onset is incomplete, an imputation algorithm will be used to classify the adverse event within the appropriate adverse event period. The algorithm for imputing date/time of onset will be conservative and will classify an adverse event as treatment emergent unless there is definitive information to determine otherwise. Details on classification of AEs with missing or partial onset dates are provided in [Section 2.6.2](#). If an AE worsens in severity, only the worst severity is captured on the AE log page in the e-CRF.

The AE log page in the e-CRF captures the date when the event became serious. If and when this date is non-missing, it indicates that the AE started as non-serious and became serious at a later date. To account for non-serious and serious parts of the AE collected in one AE log page, this AE will be split into two AEs - one non-serious, and one serious AE - with the same AE number, with the following modifications in data for these two AEs:

- Non-serious AE: AE end date, AE outcome, date of death or hospitalization, autopsy information, criterion for serious adverse event (SAE) will be blank.
- Serious AE: AE start date will use the date the event became serious.

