- Action taken towards study drug and action taken (toward AE) will be considered in relation to the date the event became serious, the last infusion date and dosing information, and a determination will be made, in consultation with safety monitor of the trial, as to whether the recorded fields belong to non-serious AE or serious AE; then the decision will be implemented in analysis. Any such decision will be rationalized in the CSR.

For treatment-emergent AEs, separate listing of AEs, SAEs and IARs that started only after the first infusion in this extension study will be provided.

Start day of treatment emergent AE relative to first infusion = Start date of AE – first infusion date + 1

Start day of treatment emergent AE relative to last infusion = Start date of AE – last infusion date + 1

Total patient year for each group will be calculated and displayed on selected AE tables.

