#### 2.4.7.1.5 *Serious adverse events*

Summary of Treatment-emergent serious adverse events will be provided by primary SOC and PT.

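### No core adverse-event table by event type is restricted to events starting in LTS13632, so extension incidence of reactions already seen in the original studies cannot be read from the pooled percentages

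*SAP*

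**What the plan says.** The primary objective (SAP 1.2.1) concerns the "safety of olipudase alfa in patients with ASMD who are exposed to long-term treatment with olipudase alfa".

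- **Observation period.** SAP 1.5 declares a change from the protocol's treatment period, made "in order to incorporate the data from original study". SAP 2.4.7 then sets the on-treatment period for all safety data as the "time from the first infusion of IMP (included) from original study to the end of the current study".
- **Default content of displays.** SAP 2.4.7: "Unless specified otherwise, the displays will include the original study data along with data collected in this study".
- **TEAE definition.** SAP 2.4.7.1.1: "AEs that started during the on-treatment period – either in this study or in the original study". Summaries give the number of events and the number and percentage of patients, with the safety population as denominator.
- **SAE table.** SAP 2.4.7.1.5: "Summary of Treatment-emergent serious adverse events will be provided by primary SOC and PT", with no limit to the extension.
- **Extension-only output.** There are two items: the overview row "TEAEs excluding original study" (SAP 2.4.7.1.2) and a "separate listing of AEs, SAEs and IARs that started only after the first infusion in this extension study will be provided" (SAP 2.4.7.1.1).
- **Other groupings.** SAP 2.4.7.1.2 adds a SOC/PT table of TEAEs by the last infusion dose before onset. SAP 2.4.7.1.6 adds tables by place of infusion, limited to events after the study's first home infusion.

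**The concern.** The documents associate the characteristic reactions with dose escalation. In the adult study the dose was raised stepwise from 0.1 to 3.0 mg/kg within 26 weeks (Protocol 4.1). Protocol 10.5.1.3.2.2 reports acute phase reactions during escalation, and 10.5.1.3.2.3 reports IL-6 and IL-8 rises with first administrations at 0.6 to 2.0 mg/kg. The rationale for Amended protocol 01 (Protocol 17.2.6) states that LTS13632 patients had already completed escalation.

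A patient percentage over both studies counts a patient once per preferred term. Someone who had pyrexia during escalation is already in the numerator, so that percentage does not change whether pyrexia recurs for years or never returns. A worst-severity row can likewise be fixed by an escalation event. At stake is whether a reader can see, by event type, how often patients had events during the period this trial was set up to observe.

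**Working it through.** The safety analysis is descriptive (Protocol 11.6.3), and the plan gives no figure to reproduce. The check is an inventory of outputs followed by arithmetic on what a pooled percentage can show.

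**1. Inventory of adverse-event outputs**

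| Output | SAP section | Limited to onset in LTS13632? |
|---|---|---|
| SOC/PT: TEAEs, worst severity, related, related by worst severity, most common | 2.4.7.1.2 | No |
| SOC/PT: TEAEs by preceding dose | 2.4.7.1.2 | No; split by dose |
| SOC/PT: protocol-defined IARs, by severity and onset window | 2.4.7.1.3 | No |
| SOC/PT: SAEs | 2.4.7.1.5 | No |
| Tables by place of infusion | 2.4.7.1.6 | No; calendar cutoff |
| One overview row, all event types together | 2.4.7.1.2 | Yes |
| Listings of AEs, SAEs and IARs | 2.4.7.1.1 | Yes |

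**2. Illustration with assumed, independent rates**

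Let p0 be the original-study incidence of an event type and p1 its extension incidence in the same patients. Pooled = 1 − (1 − p0)(1 − p1). The documents give neither rate.

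- p0 = 60%, p1 = 10%: 1 − 0.4 × 0.9 = 64%
- p0 = 60%, p1 = 40%: 1 − 0.4 × 0.6 = 76%
- p0 = 80%, p1 = 10%: 1 − 0.2 × 0.9 = 82%
- p0 = 80%, p1 = 40%: 1 − 0.2 × 0.6 = 88%
- p0 = 30%, p1 = 5%: 1 − 0.7 × 0.95 = 33.5%

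A fourfold difference in p1 moves the pooled figure by 12 points (76 − 64) or 6 points (88 − 82). Among 25 patients that is 3 or 1.5 patients. SAP 1.3 expects 17 patients, for whom it is about 2 or 1 (17 × 0.12 = 2.0; 17 × 0.06 = 1.0).

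**3. The same point without independence**

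For any dependence, p1 lies between (pooled − p0) and pooled. If p0 = 60% is known from the original study report and the pooled figure is 64%, p1 may be anywhere from 4% to 64%. If p0 = 0, both limits equal the pooled figure and nothing is lost.

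**4. What limits the effect**

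- *New event types.* Where p0 = 0 the pooled figure is the extension figure. Protocol 4.1 reports no serious or severe events in the adult study. For those patients the pooled SAE table and the severe rows therefore show extension events only.
- *Event counts.* A recurrence raises the number of events even when the patient is already counted. Scheduled exposure is mostly extension time. Taking 9 years as 468 weeks, the original-study share is 26/(26 + 468) = 5.3% for adults and 64/(64 + 468) = 12.0% for pediatric patients. At the 3-year pediatric minimum it is 64/(64 + 156) = 29.1%. These shares equal event shares only if event rates are constant.

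**5. The partial substitutes**

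- *By preceding dose.* Adults reached 3.0 mg/kg inside the original study, so original-study maintenance and late extension years share a dose column. Dose reintroduction during the extension (Protocol 8.1.1) can fall in lower-dose columns. In the main set this split covers TEAEs only, not SAEs, IARs or severity.
- *By place of infusion.* The cutoff is a calendar date. It drops earlier extension events and does not exclude later original-study events. Home patients must have a stable dose and at least 6 months without moderate or severe IARs (Protocol 10.2.1), so that column describes a selected group.

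**The case against.** The strongest reply is that pooling is a declared and reasoned choice, and exposure counted from the first infusion is a fair reading of long-term treatment. Baseline is also taken from the original study, and that study's results have their own report (SAP 2.4). With 17 to 25 patients, complete listings of extension-onset events, plus narratives for SAEs and protocol-defined IARs (SAP 2.5), let a reader follow each patient. The by-dose table addresses escalation directly, the place-of-infusion set covers severity, SAEs and IARs, and event counts register recurrences.

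Much of this stands, and it rules out several stronger readings that a reader might infer:

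- *That long-term events are tabulated nowhere by event type.* The by-dose and place-of-infusion tables do part of this.
- *That a late safety signal cannot be read from the tables.* A preferred term first seen in the extension is fully visible, and recurrences enter the event count.
- *That early reactions dominate the pooled tables.* The documents give no incidence to show this, and the adult SAE and severe rows point the other way.
- *That the primary objective is left unaddressed.* It is addressed cumulatively.

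What the reply does not supply is the patient-level extension incidence of an event type that also occurred in the original study. Listings contain the information, but the reader would have to build the table.

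**Conclusion.** The gap is real but moderate. No core SOC/PT, worst-severity, related-TEAE, SAE or protocol-defined IAR table is restricted to onset after the first LTS13632 infusion. For event types seen in both periods, extension incidence cannot be recovered from the pooled percentage, even when the original-study incidence is known (section 3 of the working). This conclusion rests on the text and needs no assumed rate.

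The size is not known. The movement of 6 to 12 points for a fourfold difference is an illustration using assumed, independent rates of 60% or 80% in the original study; it shrinks to no distortion as the original-study incidence approaches zero. The exposure shares assume full scheduled follow-up. This is a presentation gap worth closing. It does not invalidate the safety analysis.

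**What to change.** Keep the pooled tables as the cumulative view. In SAP 2.4.7.1.2, 2.4.7.1.3 and 2.4.7.1.5, add versions of the SOC/PT tables for TEAEs, related TEAEs, worst severity, SAEs and protocol-defined IARs, limited to onset after the first LTS13632 infusion. Each should show patients, events and extension patient-years. State how events ongoing at rollover are treated, and whether the extension start date of an event that becomes serious later (split under SAP 2.4.7.1.1) brings its serious part into the filter.

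Add one summary by year of exposure, limited to overall TEAEs, SAEs and IARs, with patients at risk in each year. SOC/PT tables by year are not worthwhile at this sample size because most cells would be nearly empty.

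The cost is small. The onset flag is already needed for the planned listings, and the date of the first extension infusion is already used for compliance (SAP 2.4.6.2). Patient-years would have to be recalculated from that date, since SAP 2.4.6.1 counts exposure from the original study. The downside is more output, much of it sparse.

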11.6.3.1 Adverse events

The definitions in [Section 10.5.1](#) will be used for AEs. Pretreatment AEs will be listed and presented separately from treatment-emergent AEs.

All AEs will be coded using the most recent version of the MedDRA. Adverse event incidence tables will present by system organ class (SOC) (sorted by internationally agreed order) and preferred term (PT) sorted in alphabetical order for each treatment group, and the number and percentage of patients experiencing an AE. Multiple occurrences of the same event in the same patient will be counted only once in the tables within a treatment phase. The denominator for computation of percentages is the safety population within each treatment group.

All treatment-emergent AEs, all treatment-emergent AEs potentially related to olipudase alfa, all treatment-emergent AEs leading to treatment discontinuation and study discontinuation, all treatment-emergent AEs that are IARs, all treatment-emergent SAEs (including treatment-related SAEs), and all AEs with fatal outcomes (including fatal treatment-emergent AEs) will be summarized.

Detailed listings of AEs, SAEs, AESIs, related AEs, and discontinuations due to AEs will be provided. These will include the olipudase alfa dose of the infusion prior to or during the occurrence of the AE, where applicable.

For the overall analyses of AEs, the number of AEs and annualized rate, and the number and proportion of patients experiencing specific AEs will be tabulated according to the olipudase alfa dose level of the infusion prior to or during the occurrence of the AE.

Separate analyses of AEs will also be conducted by demographic characteristics (eg, age and sex). Adverse events of special interest, such as IARs, and SAEs will be analyzed similarly.

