## 1.6 STATISTICAL MODIFICATIONS MADE IN THE STATISTICAL ANALYSIS PLAN

The SAP Version 2 was based on Amended Clinical Trial Protocol 1. This SAP is based on Amended Clinical Trial Protocol 4 (dated 31July 2019).

- The post-treatment period has been removed from [Section 2.1.3](#), since there is no pre-specified post-treatment period in the protocol.
- The paired t-test was used for testing change from baseline and/or percent change from baseline. Because the baseline value is highly correlated with change from baseline and/or percent change from baseline, the paired t-test has been changed to analysis of covariance with baseline included as covariates as indicated in [Section 2.4.8](#).
- The definition of common TEAE, TEAE of infection, Hypersensitivity IARs and TEAE of bleeding are updated in [Section 2.1.3.1](#).
- Analyses of adverse events by place of infusion was added to this SAP in [Section 2.4.7.1.6](#).
- Subgroup analyses for efficacy endpoints was added to this SAP for patients from DFI13803 in [Section 2.4.8.15](#).
- Patient narratives as described in [Section 2.5](#) will be created, to replace various data listings.

- For Physician's global assessment of change, the 7 categories will be converted to numeric values and summarized, as described in [Section 2.4.8.6](#).

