## **2.4.6 Extent of investigational medicinal product exposure and compliance**

### **2.4.6.1 Extent of investigational medicinal product exposure**

The extent of study treatment exposure will be assessed from the first infusion in the original study, and will be summarized using safety population. The duration of exposure is defined as the number of weeks between first infusion in the original study and disposition date in the study: (disposition date of the study [or the cutoff date for database lock if the patients are still ongoing] – first infusion date from original study + 1)/7. The number of infusions received and the duration of exposure will be summarized using safety population.

The distribution of weeks on study treatment (<12 weeks, >=12 weeks to <26 weeks, >=26 weeks to <38 weeks, >=38 weeks to <52 weeks, >=52 weeks to <64 weeks, etc) will be provided using number and percentage of patients by age group cohorts and overall. The total number of patient-years of exposure will also be provided.

Any overdose will be captured as an AE, and will be reported as such.

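### The SAP's by-dose adverse event table omits the annualized rate that the protocol requires and does not clearly specify exposure per dose; the home/site tables have no place-specific denominator.

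*SAP*

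**What the plan says.** Protocol 11.6.3.1, for the overall analysis of adverse events: "the number of AEs and annualized rate, and the number and proportion of patients experiencing specific AEs will be tabulated", by the dose level of the infusion before or during the event. It adds: "Adverse events of special interest, such as IARs, and SAEs will be analyzed similarly".

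The SAP's by-dose table (2.4.7.1.2) is a single sentence: "TEAEs by the latest infusion dose immediately preceding the start of AE will be provided by SOC and PT". SAP 2.4.7.1.1 sets the content of adverse event summaries as events (N), patients (n) and percentage, and states: "The denominator for computation of percentages is the safety population". It also says: "Total patient year for each group will be calculated and displayed on selected AE tables". Neither the groups nor the selected tables are named there.

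The exposure section (SAP 2.4.6.1) gives total patient-years, the number of infusions, and a distribution of weeks on treatment that "will be provided using number and percentage of patients by age group cohorts and overall". Nothing in it is split by dose or by place of infusion.

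SAP 1.5 records one departure from the protocol's statistical section, with the words "the treatment period definition is changed to". SAP 1.6, which lists changes from the previous SAP version, notes: "Analyses of adverse events by place of infusion was added to this SAP". Those tables, in SAP 2.4.7.1.6, are meant to show whether home and site infusion are comparable.

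**The concern.** Safety is the primary objective, and dose is a live safety question here. Protocol 10.5.1.3.2.2 reports acute phase reactions in 2 patients during escalation, and the Amendment 06 rationale (protocol 17.2.1) names transient transaminase elevation during escalation as an important identified risk.

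The SAP starts its observation period at the first infusion of the original study (2.1.3 and 2.4.7). The by-dose table therefore sets brief escalation doses beside the dose on which patients enter the extension and may stay for years. Without exposure, a large count at the later dose may reflect only time spent there, and a small count at an early step may hide a high rate. The protocol's annualized rate would deal with this difference in exposure.

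The home/site tables have a related weakness. A comparison of places needs to know how many infusions were given, and how many patients were infused, at each place.

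**Working it through.** The documents state no figure on this point, so there is none to reproduce. The first step compares texts; the other two are illustrations under stated assumptions.

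**1. Requirement against plan**

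- Statistic: protocol 11.6.3.1 asks for events, annualized rate, patients and proportion by dose. SAP 2.4.7.1.1 and 2.4.7.1.2 give events, patients and percentage by dose. The rate is absent from every adverse event section of the SAP.
- Exposure by dose: SAP 2.4 and 2.4.7 organize displays by original study, age cohort and overall. Dose is not named as a display group. SAP 2.4.6.1 does not split exposure by dose. The patient-years sentence in 2.4.7.1.1 could cover dose groups but does not say so.
- Declaration: SAP 1.5 lists only the treatment-period change.
- Version: the SAP follows Amended Protocol 4; the protocol supplied is Amended Protocol 07. The logs for amendments 05, 06 and 07 name no change to 11.6.3.1, and the log for amendment 04 names 11.6.4 and 11.7 but not 11.6.3.1.

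**2. Exposure at a short step and at the later dose**

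Inputs: infusions every 2 weeks (protocol 8.1.1); a step given twice, as protocol 8.1.1 describes for 0.3 mg/kg by reference to the original escalation schedule; 52 weeks per year; about 25 patients (protocol 11.2). Assumptions: every patient passes through the step and then spends one full year at a common later dose, without changes or missed infusions.

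- Time at the step: 2 × 2 = 4 weeks, or 4/52 = 0.077 patient-years per patient.
- Time at the later dose: 52 weeks.
- Ratio: 52/4 = 13. Each further full year at that dose adds another 13.
- For 25 patients: 25 × 4/52 = 1.92 patient-years at the step against 25 at the later dose.
- If each row of the table shows 10 events, the rates are 10/1.92 = 5.2 and 10/25 = 0.40 per patient-year. Equal counts then stand for rates 13-fold apart.
- Conversely, equal rates would give 13 times as many events at the later dose.

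**3. Home percentages over the safety population**

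Let x patients have an event after home infusion, k be the patients ever infused at home, and N the safety population. The default percentage is x/N; the percentage among those exposed is x/k. The first is k/N of the second. The documents do not give k, so a range is shown with x = 2:

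- k = 5: 2/5 = 40% of those exposed; 2/25 = 8% of 25 patients, or 2/17 = 11.8% of the 17 in SAP 1.3.
- k = 10, N = 25: 20% against 8%.
- k = 20, N = 25: 10% against 8%.

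SAP 2.4.7.1.6 also limits events to those after the first home infusion in the study, but plans no infusion count for that period.

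**The case against.** The strongest reply is that patient-years are already promised. A by-dose table is an adverse event table, dose levels are a natural reading of group in that setting, and patient-years on such a table serve little purpose except rates. This stands to a degree. A reader might infer that the rate could not be computed from the planned output; the documents do not support that, because if the by-dose table is among those selected, with patient-years shown by dose, the rate is one division away. What is supported is that neither the rate nor the exposure by dose is clearly specified.

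It can also be said that nothing in the SAP withdraws the protocol's rate, and that silence in SAP 1.6 proves little because that section covers changes from the earlier SAP. That is fair, so the point about declaration rests on SAP 1.5 alone. The text of Amended Protocol 4 is not supplied; the logs make a version difference unlikely but do not exclude it.

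The gain is limited too. All safety summaries are descriptive (protocol 11.6.3), by-dose rates stay confounded with time on treatment, and 0.077 patient-years per patient gives an imprecise rate. These are reasons to caveat the rate, not to leave it out unannounced.

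On home/site, the tables are an addition by the SAP, not a protocol requirement. A reader might infer that they have no denominator at all. They do: the general rule in SAP 2.4.7.1.1 supplies the safety population. A reader might also infer that home infusion will show more, or fewer, events than site infusion for reasons of exposure alone. The documents do not settle the direction. It depends on the number of home patients and their home infusions per year, and neither is given. Quarterly visits are normally at the site, but the protocol allows them at home in declared emergencies.

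**Conclusion.** The concern holds in this form: the by-dose table lacks the annualized rate that protocol 11.6.3.1 requires, exposure by dose is not clearly specified, and SAP 1.5 does not declare the difference. No test or error rate is affected. The consequence is that counts and percentages by dose, taken alone, do not show whether event rates differ by dose.

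The 13-fold figure is an illustration. It assumes a two-infusion step, one full year at the later dose, a common later dose and no dose changes. A common final dose is documented for the 5 adults (protocol 4.1), not for the children; protocol 8.1.4 permits adjustments. A longer data cut raises the ratio and a shorter one lowers it. A reader might take multiples based on the 9-year maximum as the expected size; the documents do not support that, since the SAP also serves an earlier cutoff for a regulatory submission (2.4.7.11).

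Whether the by-dose rate extends to infusion-associated reactions and serious events is ambiguous in the protocol.

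The home/site point is secondary. The default denominator includes patients never infused at home and dilutes home percentages by the factor k/N. No infusion counts by place are planned. Home patients are also selected: protocol 10.2.1 asks for clinical stability and no moderate or severe infusion reactions for at least 6 months.

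**What to change.** 1. In SAP 2.4.7.1.2, add for each dose level the patient-years (or infusions) and the annualized rate of treatment-emergent events. Do the same for infusion-associated reactions and serious events if the protocol's sentence on them is read to cover dose, and say which reading is taken. State that by-dose rates are confounded with time on treatment and imprecise for short steps. If the rate is not wanted, declare and justify the departure in SAP 1.5.
2. In SAP 2.4.7.1.6, report for each place the number of infusions over the same calendar period as the events, the patients with at least one infusion there, events per 100 infusions, and percentages over those exposed patients. Note that home patients are selected for stability.

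The cost is SAP wording and minor programming. The dose, date and place of each infusion are needed for the planned tables anyway.
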